The proposed observational study will evaluate the relationship between measures of psychopathology, disordered eating, and impulsivity, (each assessed preoperatively and in the early postoperative period) and changes in weight and psychosocial status in the first two years after bariatric surgery. Secondary outcomes of prevalence and control of T2D and hypertension, health services utilization, and adherence to antidiabetes and antihypertensive medication will also be assessed. All participants will complete assessments at baseline (before surgery) and at 6, 12, and 24 months follow-up. Secondary aims will examine psychopathology, disordered eating, impulsivity, as well as weight loss, in relation to changes in eating behavior, physical activity, psychosocial status, and substance use in the first two years after bariatric surgery. The study has one specific aim and two secondary aims. Specific Aim 1: To determine the relationship between psychopathology, disordered eating, and impulsivity assessed preoperatively and changes in body weight over the first two years following bariatric surgery. We will determine which individual measures falling under these constructs are important in predicting the relative success of bariatric surgery. We will also examine the relationship of changes in the individual measures (from baseline to 6-months after surgery) on subsequent weight loss. (The study is powered on this aim.) We predict that individual measures of psychopathology, disordered eating, and impulsivity will predict smaller weight losses two years postoperatively. We also predict that smaller changes in measures of impulsivity, psychopathology, and disordered eating within the first 6 postoperative months will be associated with smaller weight losses at postoperative month 24. Secondary Aim 1: To examine the correlation structure among our individual measures, and subsequently will generate and confirm composite measures for the three constructs. Composite measures of psychopathology, disordered eating, and impulsivity will predict smaller weight losses two years postoperatively. We also will estimate the proportion of variance in weight loss accounted for by each composite measure. We predict that confirmatory factor analysis will confirm that our individual measures represent three constructs of psychopathology, disordered eating, and impulsivity. Higher values of these composite measures will in turn predict smaller weight losses at postoperative month 24. Secondary Aim 2: To assess the relationship between baseline measures of interest and postoperative changes in caloric and macronutrient intake, eating behavior, physical activity, and psychosocial status. We predict that participants with greater psychopathology, disordered eating, and impulsivity will report greater caloric intake, less favorable changes in macronutrient intake and eating behavior, participate in less physical activity and report more symptoms of psychosocial distress.

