however, are not universal and vary between patients and across surgical procedures. It is estimated that 20-30% of patients experience suboptimal weight loss or significant weight regain within the first few postoperative years. Reasons for this are not fully understood, but likely involve both physiological processes and behavioral factors (e.g., difficulty adhering to the dietary and physical activity recommendations made prior to surgery). Extreme Obesity More than one-third of American adults are obese, defined by a body mass index (BMI) of 30 kg/m2.1 Furthermore, 8.3% of women and 4.4% of men are extremely obese, defined by a BMI 40 kg/m2.1 Obesity, and extreme obesity in particular, is associated with major health complications including coronary heart disease, hypertension, type 2 diabetes mellitus, sleep apnea, and osteoarthritis.2-4 Surgical Treatment of Extreme Obesity Bariatric surgery is currently recommended for individuals 18 years and older with a BMI of 40 kg/m2 or those with a BMI of 35 kg/m2 in the presence of significant co-morbidities.5,6 Approximately 200,000 individuals are estimated to undergo bariatric surgery in the United States each year. The most common surgical procedures include the gastric bypass (GB), sleeve gastrectomy (SG), and adjustable gastric banding (AGB).7,8 As of 2013, the GB was the most common procedure in the United States, comprising 56% of all procedures; the SG comprised 36.3%.8 Anecdotal reports suggest that the SG is increasing in popularity while the AGB is now performed infrequently. With all three procedures, patients typically reach their maximum weight loss of 20-35% of body weight 12 months after surgery.3,4,9-16 These weight losses are associated with significant improvements in obesity-related co-morbidities and decreased risk of mortality.3,4,11,17-24 Despite these impressive results, studies have found that approximately 25% of patients who undergo bariatric surgery fail to reach or maintain the expected postoperative weight loss.25-27 Courcolous and colleagues, for example, observed that 23.6% of GB patients regained weight between postoperative year 1 and year 2. Less is known about the typical postoperative weight trajectory of patient who have undergone SG. Recent studies have suggested that weight regain is associated with deterioration of many of the health benefits seen with bariatric surgery.12,28-31 Psychosocial Status and Psychopathology in Candidates for Bariatric Surgery Extreme obesity is associated with a significant psychosocial burden, including impairments in quality of life, body image, sexual behavior and other areas of psychosocial functioning.32 While this distress is believed to contribute to the decision to have bariatric surgery, its impact on postoperative outcomes is less clear. At present, little is known about the physiological and behavioral contributions to success or failure of bariatric surgery.33 Regardless, weight regain after bariatric surgery is frequently attributed to preoperative psychosocial and behavioral factors.27,34-41 More specifically, there has been a great deal of interest in the presence of formal psychopathology in bariatric surgery patients and its potential contribution to postoperative outcomes.42-45 At least six studies have described rates of psychopathology in candidates for bariatric surgery using structured diagnostic instruments.46-51 Lifetime rates of any psychiatric diagnoses ranged from 36.8%-72.6%, higher than those reported in most studies of the general population. Mood disorders were the most frequent diagnoses, seen in 22.0%-54.8% of patients. Substance use disorders (SUDs) were found in up to 35.7% of patients and alcohol abuse or dependence in up to 33.2%. Binge eating disorder (BED), defined as eating an unusually large amount of food within a short period of time coupled with a loss of control over eating, has been diagnosed in 4.6% to 27.1% of patients. Current diagnoses (as compared with lifetime) were less common, reported in 20.9%-55.5% of candidates for surgery. Mood disorders were diagnosed in up to 31.5%. BED ranged from 3.4%-41.9%. Current substance use was seen in less than 2% of patients. (Note. The lower percentages of those with current psychopathology, as opposed to lifetime psychopathology, are expected.) While studies of the psychosocial characteristics of bariatric surgery candidates have been informative, they are not without limitations. Many studies have suffered from methodological concerns, including small sample sizes or lack of an appropriate comparison group. Further, establishing psychiatric diagnoses prior to bariatric surgery is challenging. Perioperative guidelines suggest that patients undergo an evaluation with a mental health professional prior to surgery3 and most third party payers require these evaluations. However, most programs do not use structured clinical interviews to establish diagnoses for clinical purposes.52,53 Several studies have suggested that candidates for bariatric surgery engage in impression management prior to surgery, in which they minimize reports of psychopathology to present themselves to the bariatric team in the most favorable light.54-56 To address this issue, assessment of psychiatric symptoms for research purposes is recommended to occur independently from the required clinical evaluation, as we will do in the proposed study. Nevertheless, studies focusing on the relationship between specific diagnoses and postoperative outcomes may fail to account for other psychological constructs that may be shared across diagnoses. Mood disorders, BED, and SUDs all share the common psychological construct of impulsivity, considered an important aspect of executive functioning. A lack of impulse control may contribute to the excessive weight gain seen in extreme obesity and may impact the results of bariatric surgery. Disinhibition and Impulsivity among Persons with Extreme Obesity Studies have suggested that individuals with obesity, and in particular those with extreme obesity presenting for bariatric surgery, show some deficits in executive functioning. For example, candidates for bariatric surgery have shown deficits in working memory, mental flexibility, motor speed and complex attention.57,58 These deficits could impact comprehension and retention of information presented to patients during the preoperative consultation process and, thus, negatively impact the ability to adhere to the dietary and behavioral changes required for an optimal postoperative outcome.45 At the same time, metabolic dysregulation, such as insulin resistance or hyperglycemeia seen in type 2 diabetes, also is associated with cognitive deficits, suggesting a potential physiological mechanism for the relationship.59-61 Dietary disinhibition, defined as a loss of control over eating, plays a central role in the overconsumption of food and, subsequently, the development of obesity.62.63 Disinhibition is similar to impulsivity, the term more commonly used in the substance use and smoking cessation literatures. Impulsivity is a multi-faceted construct and refers to the absence of the ability to inhibit an automatic behavior (otherwise known as response inhibition)64,65 and the tendency to discount future consequences in favor of more immediate outcomes (known as delay discounting).66,67 Similar to the role of disinhibition in obesity, impulsivity contributes to the development of and relapse with SUDs. Indeed, response inhibition and delay discounting are associated with both SUDs68-70 and obesity.71,72 Both also predict response to treatment for both SUDs73-75 and obesity.76 Chronic overeating and binge eating share several neurobiological and behavioral similarities with SUDs.77,78 In this regard, both may be viewed as behavioral disorders, in which intake (of food, alcohol, and/or drugs) escalates to a rate that is unhealthy and maladaptive. Nevertheless, the specific nature of the relationship between binge eating and substance use remains to be fully elucidated.79 There are similarities between binge eating and addictive disorders, including craving for the desired substance (drug or highly palatable food), a sense of loss of control when using, repeated attempts to control use despite clear adverse consequences, and the dedication of much time in obtaining and using the substance.80-82 Thus, the disinhibition observed with obesity and binge eating, the impulsivity seen with substance use disorders, and the emotional dysregulation associated with mood disorders all likely share commonalities (dashed lines in Figure 1) that may both contribute to the development of extreme obesity and also may be associated with weight loss (solid lines in Figure 1) and changes in psychosocial status after bariatric surgery. Psychosocial Status and Psychopathology after Bariatric Surgery In general, individuals who undergo bariatric surgery report dramatic improvements in psychosocial status and functioning postoperatively.83,84 The vast majority of patients report significant reductions in symptoms of depression and anxiety in the first postoperative year. They also report significant improvements in health and weight-related quality of life. Patients also report improvements in body image, sexual functioning, and relationship satisfaction.85-87 The relationship between preoperative psychopathology and postoperative outcomes is less robust.34,84 Livhits and colleagues reviewed this literature and concluded that the preoperative factors of BMI, BED, and the presence of personality disorders provided the strongest negative associations with postoperative weight loss.42 At least two studies have suggested that preoperative psychopathology, particularly mood and anxiety disorders, is associated with smaller weight postoperative weight losses.88,89 The relationship between BED and postoperative weight loss is unclear; some studies have found a relationship between preoperative BED and postoperative weight loss90.91 while others have not.92-94 Additionally, two studies have suggested that a history of substance abuse is associated with larger weight losses following bariatric surgery.95.96 The interpretation of this counterintuitive finding is that the selfregulation skills that help patients maintain their sobriety also help patients adhere to the demands of the recommended postoperative diet. Disinhibition and Impulsivity following Bariatric Surgery Encouragingly, studies have shown that there are improvements in executive functioning in persons with extreme obesity in the first two years after bariatric surgery.97,98 Postoperatively, patients typically report decreases in disinhibition and hunger, as well as increases in cognitive restraint.99,100 The physical aspects of bariatric surgery typically prevent individuals from eating the objectively large amount of food necessary to meet the diagnostic criteria of BED. However, many individuals continue to report the feeling of loss of control over their eating.44 The self-reported inability to control these impulses postoperatively is associated with smaller weight losses and greater emotional distress in the first few postoperative years.91,99,101,102 There is additional evidence that patients have difficulty with impulse control after surgery. A number of studies have suggested that there is an increased risk of substance abuse following bariatric surgery.101,103,104 King and colleagues,105 in their seminal investigation, found an increased rate of alcohol use disorder in the second postoperative year as compared to the year prior to surgery or in the first postoperative year. Other recent studies also have found increases in alcohol or composite substance abuse (drug, alcohol, or cigarettes) in the first two years after bariatric surgery.106-108 Postoperative substance use has been associated with smaller postoperative weight losses, postoperative nocturnal eating, and subjective hunger.109 Patients at

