
Characteristics of the Study Population

Target population

Adults aged 18-65 years old who plan to undergo one of two bariatric surgeries, either Rous-en-Y Gastric Bypass (RYGB) or Laparoscopic Sleeve Gastrectomy (LSG) at the University of Pennsylvania Health System. Based on our previous studies of bariatric surgery patients, we expect that approximately 80% of participants will be women and 20% of participants will be ethnic minorities.

Subjects enrolled by Penn Researchers 300

Subjects enrolled by Collaborating Researchers

0

Accrual

Participants will be recruited from the Bariatric Surgery Programs at the Hospital of the University of Pennsylvania and Presbyterian Medical Center, all part of Penn Medicine. We will enroll participants until a total of 300 adults have completed baseline visits. We anticipate that we will need to consent a larger number of participants in order to meet this enrollment goal. Based on our previous studies of bariatric surgery patients, we expect that approximately 80% of participants will be women and 20% of participants will be ethnic minorities. [name], Director of the Bariatric Surgery Program, conducts approximately 300 bariatric surgery operations per year. Additional surgeons in the Bariatric Surgery Program (at the Hospital of the University of Pennsylvania, Presbyterian Medical Center, and Pennsylvania Hospital) operate on approximately 200 patients per year. In order to increase the diversity and size of our sample, participants will also be recruited from the Temple Health Bariatric Surgery Program. The patient flow at Temple Health is similar to that of the Penn Health System (described below). Participants will be approached by the Research team during their pre-operative testing and education process.

Key inclusion criteria

We seek to enroll a sample of patients that is representative of those who present for bariatric surgery. We have based our exclusion criteria for the study largely on the clinical criteria used for bariatric surgery as well as our previous studies with bariatric patients. Inclusion Criteria: Adults aged 18-65 years old 18 years of age or above BMI of 35-60 kg/m2 (or 35 kg/m2 in the presence of significant weight-related comorbidities, including established coronary artery disease, established peripheral arterial disease, symptomatic carotid artery disease, sleep apnea, metabolic syndrome, cardiomyopathy, hypertension, and debilitating joint pain).

Key exclusion criteria

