
The following documents are currently attached to this item:

There are no documents attached for this item.

Deception

Does your project use deception? No

Analysis Plan

Analysis will be conducted using Stata 13.0 (Stata Corporation, College Station, TX). After the completion of quality assurance procedures, descriptive statistics will be summarized for all patients by predictor group (dichotomized). Data screening: Prior to performing analyses, standard data screening/ cleaning procedures will be applied. These procedures will: screen the data for data-entry errors; check for outliers; assess the extent and pattern of missing data; create all summary scores needed for analysis; and check that appropriate assumptions of normality are met. In all analyses, the assumptions underlying the application of all the statistical methods that are used will be examined, principally through the use of standardized residuals, influence diagnostics, and graphical displays. Image processing will include image quality assessment procedures that examine global and region of interest (ROI) based raw and processed temporal signal-to-noise ratio, absolute and relative motion, and signal spike count. Potential outliers will be identified in the cumulative sample by examining quality assessment measures and flagging for further investigation subjects greater than two standard deviations from the mean on any one measure (i.e., behavioral performance, image distortion and artifact, general linear model fit). The purpose of this evaluation is to determine whether the time series is likely valid, and, if so, it will remain. Otherwise it will be corrected, if feasible, or removed from the analysis. The final sample will be examined in a similar fashion to determine whether any subjects warrant data cleaning or require exclusion from the final statistical analysis. Analysis of repeated measures: Our four-session within-subject design will generate multiple outcome measures that belong to the Gaussian family, and we will therefore use standard repeated-measures analysis of variance (ANOVA). Imaging outcomes (perfusion and BOLD) will be modeled using standard voxel-based image analysis techniques (described below) that incorporate random effects. Other outcomes (weight loss, ratings) will be modeled using a linear mixed-effects models framework, using using Stata 13.0 (Stata Corporation, College Station, TX). We could use a population averaged approach such as generalized estimating equations. However, the mixed model approach will provide the flexibility to allow for different error variances for different sessions if necessary. Voxel-based image analysis has limited flexibility, particularly when adding multiple covariates and interaction. When needed, summary values (e.g., mean rCBF, mean BOLD% signal change) extracted from ROIs will be modeled in STATAs mixed-models framework. These models can be extended to include additional explanatory variables (e.g., weight change, heart rate, respirations, age). Primary Aim 1 We will take a mixed models approach. The main interest in this study is the Group x Time interaction, where Group will be a between-subjects factor and Time will be a categorical within-subjects factor. This can be interpreted as population averages (GEE fitting method). Hypothesis 1: We will fit a 2 (Group: Dichotomized Baseline Measures, Low, High) x 3 (Time: change from baseline to month 6, 12 and 24) mixed-effects model for change in weight. Hypothesis 2: We will fit a 2 (Group: Dichotomized difference scores, 6 Month minus Baseline, Low, High) x 2 (Time: change from baseline to months 12 and 24) mixedeffects model for change in weight. In addition, the mixed effects models will include adjustments for surgical procedure, gender, and time since surgery. We recognize that the change in weight could also be associated with effects of several pertinent patient characteristics. To this end, we will consider additional covariates (e.g. sociodemographic variables, comorbidities, medication use, tobacco use, and initial weight). For both hypotheses, we will explore the continuous version of our predictor variables, where in place of Group, we use the real values of the predictor. This yields a difference of slopes with respect to predictor value across time points. Secondary Aim 1 We will use confirmatory factor analysis to verify our expected natural groupings of individual measures into composite measures. We will specify 3 factors and use Varimax rotation. We will assemble composite scores for each of our constructs by summing the standardized score values. We will then standardize the composite score and outcome (change in weight at 24 months). We will estimate the partial correlations (direct and indirect) among individual measures, composites, and outcome in a path analysis as suggested by Figure 1 to estimate the fraction of variance in outcome accounted for by each of the constructs. Secondary Aim 2 The outcomes will consist of (continuous) changes in behavior from baseline. We will use correlation to examine the relationship of baseline impulsivity measures to changes at 6, 12 and 24 months. The exception is changes in diet composition. In this analysis, we will use multivariate regression methods,

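### The Secondary Aim 1 path analysis names no adjustment for surgical procedure or gender, so each construct's share of weight-loss variance may be inflated or masked if the composites differ by procedure or gender

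*Combined protocol and SAP*

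**What the plan says.** All references are to the combined protocol and SAP.

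- **Analysis Plan, Primary Aim 1.** After the two hypotheses the plan states: "In addition, the mixed effects models will include adjustments for surgical procedure, gender, and time since surgery". It goes on to say that "we will consider additional covariates (e.g. sociodemographic variables, comorbidities, medication use, tobacco use, and initial weight"). Both statements sit in the Primary Aim 1 text, and the first is limited by its own words to the mixed models.
- **Analysis Plan, Secondary Aim 1.** The method changes to a factor analysis, summed composites and a path analysis. The outcome is weight change at a single time point: "We will then standardize the composite score and outcome (change in weight at 24 months"). The variables listed are those in "We will estimate the partial correlations (direct and indirect) among individual measures, composites, and outcome in a path analysis as suggested by Figure 1", and the purpose is "to estimate the fraction of variance in outcome accounted for by each of the constructs". No covariate is named, and no general sentence carries the Primary Aim 1 adjustments over.
- **Objectives, Overall objectives, Secondary Aim 1.** The matching aim reads "We also will estimate the proportion of variance in weight loss accounted for by each composite measure". It names no adjustment either.
- **Target population.** Participants plan to have "either Rous-en-Y Gastric Bypass (RYGB) or Laparoscopic Sleeve Gastrectomy (LSG"). The section on assigning subjects to groups says there is no randomisation and that surgery is not a study procedure.
- **Background.** Outcomes of surgery "are not universal and vary between patients and across surgical procedures".
- **Figure 1.** The figure is not available in the text reviewed. The Background mentions dashed lines for what the constructs share and solid lines to weight loss. It mentions no procedure or gender element.

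**The concern.** For weight change after surgery, the plan treats procedure and gender as important enough to fix as adjustments in the primary analysis. The variance-share analysis uses the same outcome at month 24 and does not mention them.

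Nothing in the design balances the composites across operations, because patients and surgeons choose the operation. Suppose patients with more psychopathology, disordered eating or impulsivity receive one operation more often, and that operation yields a different weight loss. Part of the procedure effect would then be credited to the psychological construct, or would hide the construct's own contribution. The same reasoning applies to gender if both the composites and weight loss differ by gender.

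At stake is the reading of Secondary Aim 1: how much each construct accounts for, and which accounts for most. The results would also differ in adjustment from the Primary Aim 1 results for the underlying measures.

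**Working it through.** The plan states no R-squared, power or alpha figure for Secondary Aim 1, so there is no figure to reproduce. The check asks what leaving out a covariate does to a construct's share.

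**Inputs.** From the documents: two pooled procedures, about 80% women expected, and 300 completed baseline visits. Every effect size and correlation below, and the 50/50 procedure split, is an assumption.

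**Step 1: one composite, one covariate.** Score the outcome Y so that higher means more weight lost. With all variables standardized, Y = b·C + g·P + e, where C is the composite, P is procedure (higher for the one with larger loss) and c = corr(C, P).

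- Unadjusted correlation: r = b + g·c, so the unadjusted share is (b + g·c)².
- Adjusted share, as the increment in R-squared over P: b²·(1 − c²).

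Take b = -0.20:

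| g | c | r | Unadjusted share | Adjusted share |
|---|---|---|---|---|
| any | 0 | -0.20 | 4.00% | 4.00% |
| 0.2 | +0.1 | -0.18 | 3.24% | 3.96% |
| 0.2 | -0.1 | -0.22 | 4.84% | 3.96% |
| 0.2 | +0.2 | -0.16 | 2.56% | 3.84% |
| 0.2 | -0.2 | -0.24 | 5.76% | 3.84% |
| 0.3 | +0.1 | -0.17 | 2.89% | 3.96% |
| 0.3 | -0.1 | -0.23 | 5.29% | 3.96% |
| 0.3 | +0.2 | -0.14 | 1.96% | 3.84% |
| 0.3 | -0.2 | -0.26 | 6.76% | 3.84% |

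To judge whether these assumptions are plausible: at a 50/50 split the SD of a binary covariate is 0.5. So g of 0.2 to 0.3 is a gap between procedures of 0.4 to 0.6 SD in weight change (g/0.5). A correlation of 0.1 to 0.2 is a gap of 0.2 to 0.4 SD in the composite (c/0.5).

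**Step 2: three composites.** The plan has three constructs, so a large simulation (n = 2,000,000) was run. It assumed inter-composite correlation 0.3, path -0.15 for each composite, standardized gender effect 0.2, procedure effect 0.3, an 80/20 gender split and a 50/50 procedure split. The figures are each composite's unique share, unadjusted and then adjusted for both covariates:

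- Composites unrelated to procedure and gender: 1.9% and 1.9% for all three.
- One composite 0.5 SD lower in the procedure with larger loss: 4.8% and 1.8% for that one; 1.5% and 1.9% for each of the other two.
- The same composite 0.5 SD higher instead: 0.4% and 1.8% for that one; 2.5% and 1.9% for each of the other two.
- All three 0.5 SD lower by procedure and 0.3 SD lower by gender: 3.5% and 1.8% each.

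**What this shows.** Omission can inflate, deflate or leave a share unchanged. When one composite differs by procedure, the shares of the other two move as well, so three constructs with equal paths can appear ranked. With no correlation, procedure and gender variance goes to the residual and not to any construct.

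**The case against.** Several points on the other side stand.

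- **Bias is conditional.** A reader might infer that every construct's share necessarily absorbs procedure and gender differences. The documents do not support that. It requires a composite to be correlated with procedure or gender, and no section says that any is.
- **Figure 1 is unseen.** A reader might infer that the path model is known to exclude these covariates. Only the text can be judged. It names none, and the one-sentence description of the figure mentions none, but that is not a full account of the figure.
- **The gender part is thinner.** The Background supports outcome differences by procedure, in words only. Nothing says weight loss or the composites differ by gender. The support is the plan's own choice to adjust for gender in Primary Aim 1.
- **An unadjusted share is a legitimate quantity.** In a study of predictors it describes what the composite accounts for, by whatever route. If psychopathology influences the choice of operation, adjustment removes part of that route. The plan does not say which share it wants.
- **A false-positive claim would go too far.** One might compute an inflated rejection rate at 300 patients. The plan specifies no significance test for this step, and 300 counts baseline visits, with dropout expected.
- **Comparability is limited anyway.** Primary Aim 1 centres on dichotomized individual measures over time, and Secondary Aim 1 on standardized composites at month 24. Shared covariates would align the adjustment, not the scale.

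These points limit the claim without removing it. The plan itself treats both variables as necessary adjustments for this outcome, and reporting both shares keeps the descriptive quantity.

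**Conclusion.** The concern holds in a conditional form. As written, the Secondary Aim 1 path analysis does not include procedure or gender, although the plan adjusts for both when modelling the same weight outcome. Each construct's share may be inflated or masked to the extent that the composites differ by procedure or gender, and is unbiased if they do not.

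Under the single-composite assumptions, the unadjusted share runs from 1.96% to 6.76%, against 3.84% to 3.96% adjusted. These figures illustrate sensitivity and do not predict the trial's result. They use a simple correlation with one composite, whereas the plan specifies partial correlations among three constructs.

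In proportion: the shift in the correlation is |g·c| = 0.02 to 0.06. The standard error of a Fisher-transformed correlation with all 300 patients is 1/√297 = 0.058, and it would be larger after dropout. The shift is thus at most about one standard error here, but unlike sampling error it does not shrink with more patients. This is a secondary aim and the primary analysis is unaffected. The change is still worth making because it costs almost nothing.

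**What to change.** In the Secondary Aim 1 paragraph of the Analysis Plan:

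- Enter surgical procedure and gender as exogenous covariates in the path model, with paths to 24-month weight change and free covariances with the constructs.
- Report each construct's share as the increment in R-squared over the model containing those covariates.
- Report the unadjusted share alongside, labelled as descriptive.

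The cost is a sentence or two in the plan and two covariates in one model. Type of surgery is already extracted from the medical record and gender is already a planned covariate. The adjusted shares may be slightly less favourable than the unadjusted ones.
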